## 8. Prior Approvals

Departmental Approval form included.

## 9. Multi-Site Research NA

## 10. Study Procedures

Specific Aim 1.1: Acute effectiveness of tDCS in mmTBI

### Experimental Design and Methods

**Participants:** Eighty TBI subjects will be recruited for this study, all having suffered mild or moderate TBI (mmTBI, as defined before) at least 3 months prior to study enrollment, but not more than 15 years prior to enrollment. 80 age- and sex-matched healthy controls will be recruited. All participants will be 18-55 years of age. We will expect to screen approximately 120 patients with mmTBI in order to reach our goal of 80 TBI subjects. The experimental pre-post, double-blind design is graphically displayed. It includes randomization of TBI patients to either a left-sided active transcranial direct current stimulation (tDCS) protocol, or sham treatment group to foster isolation and identification of any tDCS treatment effects. To enhance our statistical power to identify predictors of treatment response in mmTBI patients, 40 TBI subjects and 40 controls will be assigned to each group: left-sham and left-active.

**Recruitment:** Recruitment primarily will be through the UNM Hospital Emergency Department (ED) (the only Level 1 trauma center in New Mexico). The UNM Health Sciences Center (HSC) Clinical and Translational Science Center (CTSC) Participant Recruitment Service (PRS) for Clinical Research will monitor ED intake records for patients who meet criteria once released from the hospital, then notify the study team of these cases. A second means of recruitment will involve direct referrals from UNM and non-UNM ED physicians and/or referrals from any clinic in the Albuquerque metropolitan area, via the distribution of flyers and calls to clinical directors to publicize the study. A third means of recruitment will involve information listed on the UNM CBRR and MRN websites, and posted flyers.

**PROTOCOL TITLE:** Transcranial direct current stimulation for treatment of deficits after traumatic brain injury.

[figure not shown]
Subjects who meet initial criteria for inclusion will be contacted by a member of the research team and invited to enroll in the study. Interested patients will be invited to the offices of the Center for Brain Recovery and Repair clinical core for formal screening procedures. A brief structured interview will be administered along with the NSI. If potential participants do not meet study criteria, they will be thanked for their time and identifying information recorded for future reference. Subjects with a legally authorized representative (LAR) will be excluded from the study, and all participants will be screened for LAR. All participants will be adults (ages 18-55), and all participants will consent for themselves. Although participants will be recruited from referral or from emergency department (or other) records, no participant will be enrolled in the study without being given sufficient opportunity to consider whether or not to participate. In most cases, they will undergo multiple interactions with study personnel over the course of days, and during each they will have the opportunity to ask questions and discuss their decision to participate. They will have multiple opportunities to reconsider any decisions during the screening and consent process, minimizing the possibility of coercion or undue influence by the researchers. If potential participants successfully meet basic study criteria, they will be invited to undergo consent procedures and enrolled in the study. All participants will be fluent in English, and the information contained in the consent form will be discussed with them in addition to their having a written description of the study in the form, to assure that they truly understand the study procedures.

Randomization will occur at time of consenting. The study coordinator who consented the patient will use a coin-tossing procedure to determine whether the subject is assigned to the active group (group 1) or control group (group 2). Modifications will be made as necessary toward the end of enrollment to ensure equal group size and balanced distribution of demographic variables such as age and gender. The study coordinator will not be blinded to group assignment, and with the assistance of the Clinical Core, will program the TDCS devices to deliver active or sham stimulation depending on which group the subject has been assigned. However, the coordinator will not be involved in performing any stimulation procedures. The study technician and principle investigator, who will be responsible for administering the stimulation, will not be aware of which group receives active versus control, and will thus be blinded, as the TDCS device will only display the group number (1 or 2).

Once group membership is determined, individual participants may undergo demographic data collection, neuropsychological assessments and tDCS treatment sessions. They may also undergo EEG and/or MRI. Direct identifiers of participants will be maintained on a separate database that will be stored behind locked doors, in a locked filing cabinet in a secure area of the Clinical Core.

**Demographic Data:** As part of the initial assessment, basic demographic data regarding the subject may be noted down, including age, gender, socioeconomic status, educational attainment, handedness, use of common stimulants such as caffeine, and brain injury severity. They may also be asked if they are willing to allow their medical record to be accessed, for the purposes of confirming details about any TBI as well as obtaining results of neuroimaging studies done at the time of injury or afterward. This will include medical, surgical, neurological and psychiatric history, results of lab tests, brain scans, electroencephalography tests, medication lists, information from doctor's visits and hospital visits.

**Neuropsychological testing procedures:** All neuropsychological testing will be administered in the Center for Brain Recovery and Repair Core by trained study personnel under direct supervision of core directors, clinical neuropsychologists Drs. [name], [name], or the PI. The primary dependent outcome variables to be studied are the three composite scores generated by

PROTOCOL TITLE: Transcranial direct current stimulation for treatment of deficits after traumatic brain injury.

the Examiner battery (e.g. Cognitive Control, Fluency, and Working Memory). The following domains and tests will be administered: Executive Abilities: Measures and Instruments for Neurobehavioral Evaluation and Research (Examiner); Digit Span; Delis-Kaplan Executive Function Systems (DKEFS) Trailmaking Test Conditions 2 and 4; Hopkins Verbal Learning Test (HVLT); Frontal Systems Behavior Scale (FrSBe); Test of Memory Malingering (TOMM); Wechsler Test of Adult Reading (WTAR); Digit Symbol Coding; Handedness; Socioeconomic Status (SES); Neurobehavioral Symptom Inventory (NSI); PROMIS-29 profile; Glasgow Outcome Scale-Extended (GOSE).

*Resting and task-related electroencephalography:* Electroencephalograph (EEG) may be done after neuropsychological testing in a subset of subjects. The participant will wear a cap during the EEG to record brain waves. EEG setup takes between 10 and 30 minutes, and subsequent recording takes one to two hours. During EEG assessments participants will complete numerous active tasks. Each task is designed to parse different cognitive mechanisms that contribute to adaptive performance. In perceptual tasks, participants will discriminate tone pitches amongst novel distracting tones. In decision making tasks, participants are required to classify stimuli based on pre-determined types of rules. For learning tasks, participants are asked to select among two or more pictures on the screen by pressing a button on the keyboard or gamepad, they are then presented with a reward ('+1') or not ('0') following their choice. For memory tasks, participants will view stimuli one at a time on the computer screen, and will be probed on their memory of these stimuli after a short delay. Some tasks alter the fidelity of the stimuli to make decisions more difficult, others alter the perceptual-motor mappings to make response selection more difficult, and others simply probe risk and reward preferences.

*Magnetic resonance imaging:* MRI scan(s) will involve simultaneous functional or cognitive tasks, including sequences assessing diffusion tensor imaging (DTI), magnetic resonance spectroscopy (MRS), functional MRI (fMRI), and structural sequences. Total scan time, including participant setup and removal, is expected to take 1.5 hours. Based on the study by Gasparovic et al in 2009 examining MR spectroscopy in mild TBI, utilizing an effect size of 1.27, a planned sample size of 30 subjects receiving MRI will achieve 80% power to detect a difference between groups. Participants may lie down on a table and be placed into a long donut-shaped magnet. During the scan, participants will be shown pictures and/or words and will be asked to make decisions about the information presented in them. No contrast will be used. Any female over 18 who thinks she may be pregnant will complete a urine pregnancy screen before the MRI scan. Results of pregnancy screens will be kept strictly confidential as per MRN policy. Urine samples will be disposed of immediately after testing.

*Left DLPFC anodal tDCS Intervention:* On the same day as assessment or the next day, participants will receive either active left anodal tDCS for a total of 30 minutes or sham for an equivalent duration, each day for up to ten consecutive weekdays. Current will be ramped up over 1 minute at initiation and ramped down over 1 minute with termination.

A NeuroConn tDCS (investigational) machine will be used to administer tDCS current. Targeting of the left DLPFC (F3 position, International 10-20 system of EEG coordinates) may be done by (1) locating the vertex (Cz) at the midpoint of the nasion-ion line and the midpoint of the preauricular-preauricular line; (2) locating M1 at 20% of the Cz-preauricular distance, measured from Cz; (3) locating F3 5 centimeters anterior to M1 in the horizontal plane. This method has been shown to be suitable for tDCS electrode targeting of left DLPFC. The Beam F3 method may also be used, which yields equivalent or better accuracy. Square-shaped solution-soaked or gel-soaked sponge electrodes, held by a rubber casing, are applied to the scalp using elastic bandage material. The anode will be placed on the scalp over the F3 target location and the cathode placed on the right upper arm

PROTOCOL TITLE: Transcranial direct current stimulation for treatment of deficits after traumatic brain injury.

below the deltoid. Current for the treatment condition will be applied at 2.0 mA for a total delivered charge of 60 mA-min.

*Safety of stimulation.* During tDCS application, subjects will describe physical sensations such as tingling or itching using a 10-point anchored Likert scale. Administration of tDCS will be stopped immediately if subjects report a 7 or above for discomfort, or if subjects wish to stop at any time. Subjects will also have their mood, energy, pain, and arousal levels assessed using visual analog 10-point scales. These checks will occur every ten minutes during the stimulation session.

*Double blind design and sham treatment:* The sham stimulation (control) group will receive up to 0.2 mA current for 30 minutes each session, with an initial ramping up and down of stimulation to mimic active stimulation. The sham current is used as a control condition, rather than the absence of stimulation, to equate aspects of the procedure (preparation and application of electrodes, attachment with adhesive strips, etc.), and to give the participant a degree of physical sensation that is somewhat similar to that of the 2.0 mA stimulation group while remaining well below the level sufficient to affect brain function and behavior. To accomplish a double blind, the tDCS machine is programmed to randomize sham versus active stimulation and keeps track of the stimulation protocol for later downloading.

*Cognitive control Tasks:* Participants may be administered the cognitive training battery for 30 minutes, during treatment and sham. Session procedures will begin with tDCS electrode placement while seated in a comfortable chair. After initiation of tDCS, the cognitive training will be administered on a laboratory computer. The two tasks will be presented for 15 minutes each, in counterbalanced alternating order over the ten sessions. The tasks to be coupled with tDCS are the AX-CPT (set shifting/response inhibition) and a dual auditory/visual N-back task (working memory), and were selected based on their activation of the critical neural networks associated with the three executive functions of interest. AX-CPT is a continuous performance task in which subjects must respond to specific paired letter combinations (A followed by X) with a button press while inhibiting response to non-target combinations (AY, BY, BX) (Figure 8). The dual N-back task is a continuous performance test in which subjects respond to simultaneous sequences of visuospatial and auditory stimuli being presented that match preceding stimuli n-steps earlier in the sequence.

Specific Aim 1.2: Persistence of tDCS effects and quality of life

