## 1. Objectives

Our long-term goal is to develop safe and effective treatments for symptoms of mild to moderate TBI (mmTBI) that restore patients to higher levels of functioning, decrease disability, and promote brain healing. The objective of this application is to investigate the use of transcranial direct current stimulation (tDCS) to treat symptoms of executive dysfunction and depression in patients with mmTBI. Our central hypotheses are (1) tDCS paired with relevant cognitive training facilitates improves executive function on NIH-approved neuropsychological measures, (2) tDCS reduces depression scores on NIH Common Data Elements for TBI, (3) that these improvements in emotion and cognition will be detectable up to one year after stimulation, (4) (4) certain clinical variables will reliably predict response to tDCS, such as age, education level, injury severity, and magnetic resonance imaging (MRI) evidence of structural/functional/metabolic abnormalities and (5) quantitative electroencephalography (EEG) will demonstrate changes in frontal midline theta band power and theta band synchrony, markers of cognitive control, in responders. These objectives were formulated based on our clinical experience with [name] (project mentor) characterizing symptomatic patients with mmTBI in the post-acute setting, groundbreaking research led by [name] (project mentor) that has demonstrated robust increases in attention and learning with tDCS, and extensive evidence accumulated by co-junior investigator on the grant application [name] on EEG measures of executive dysfunction.

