#### Experimental Design and Methods

*Participants:* TBI subjects from Aim 1.1 will be carried forward for study in Aim 1.3. Key clinical variables in the study group will be analyzed for association with tDCS effect, namely, lesser post-traumatic symptom burden as measured by the NSI, mild versus moderate severity of TBI, lack of neuroimaging abnormalities on MRI, and higher premorbid level of intelligence as measured by the WTAR, as these are factors shown to predict better recovery from TBI.

Specific Aim 2.1: Effectiveness of tDCS for depression after mmTBI

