### Specific Aim 2.2:

The subjects from Aim 2.1 will be automatically included. At 6 months and 1 year after stimulation, subjects will be contacted via telephone and administered the depression assessment tools utilized before, immediately after, and 1 month after stimulation.

**Specific Aim 2.3:** Subjects from Aim 2.1 will be carried forward for study in Aim 2.3. Patient and injury characteristics will predict positive response to tDCS, namely, higher premorbid intellectual function (WTAR), lesser severity of injury (mild versus moderate), lack of neuroimaging abnormalities on MRI, and more severe pre-stimulation depressive symptoms (BDI, HAM-D). Understanding which of the clinical variables described above moderate the efficacy of tDCS in mmTBI will allow for more precise patient selection and better overall efficacy in future applications.

Each of the 80 participants will receive \$20/hr in the form of cash cards for taking part in the study.. This is felt to be a fair amount that is not coercive and will help decrease attrition for this study which involves many visits.

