Statistical analyses will utilize the CTSC Biostatistics core. Power analyses and statistical analysis strategy were determined with our statistician [name], who will continue to provide recommendations and support throughout the project. Sufficient group sizes were determined on the basis of data derived from preliminary studies. Clark and colleagues found an effect size of Cohen's  $d = 1.2$  for tDCS to induce improvements in cognition. For our power calculations we will assume a more conservative effect size of  $d = 0.7$  which is consistent with a recent meta-analysis of tDCS effect sizes. With 40 tDCS treatment patients compared to 40 sham patients and an effect size of 0.7, we have 80% power to detect effects of active versus sham treatment in a two-sample t-test. Power in the linear mixed model analysis should be superior that that of the t-test. For Aim 1.1, the central analyses evaluate group (active vs. sham) differences in the EEG data and on the three Examiner composite variables across the three initial time points (before, immediately after, and 1 month after tDCS stimulation protocol). To test this hypothesis, three separate linear mixed models analyses will be performed using the three Examiner composite scores (Fluency, Cognitive Control, Working Memory) as dependent variables. In each analysis, we will incorporate three covariates that may predict variation in learning (severity: mild vs. moderate, premorbid intelligence: WTAR score, and symptom burden: NSI). This will allow us to determine predictors of treatment response (Specific Aim 1.3). Sex, ethnicity, and age will also be entered into the statistical model. The effects of these covariates will be estimated by constructing appropriate contrasts in model effects. A similar set of analyses will evaluate group differences on the variables assessed in our long-term oral/phone follow-up (five data points: (1) before tDCS, (2) immediately after tDCS, (3) 1 month post-tDCS, (4) 6 months, and (5) 1 year) for Aim 1.2. For these analyses dependent variables will be the total cognitive items score of the NSI and the PROMIS-29 profile total score). Significant effects will be followed up with more fine-grained analysis of the components of composite scores. The use of linear mixed-models minimizes the adverse impact of a missing data point, which may well occur in a longitudinal clinical study such as this. Expected attrition will be taken into account with an intention-to-treat analysis. Missing data patterns will be analyzed to assess the extent to which they are informative (in contrast to missing at random), and analyses adjusted accordingly. All EEG data will undergo standard preprocessing (e.g. motion correction, spatial normalization) and quality control prior to statistical modeling. Depending on the specific question of the study, data may be analyzed using the general linear model, independent components analysis, machine learning techniques, or a variety of other standard approaches for neuroimaging data.

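### Group sizes, healthy controls included, are justified by power to find predictors of tDCS response in mmTBI, but controls sit outside that analysis and no moderation term is specified

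*Combined protocol and SAP*

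**What the plan says.** Section 10, Participants, gives the reason for the group sizes: "To enhance our statistical power to identify predictors of treatment response in mmTBI patients, 40 TBI subjects and 40 controls will be assigned" to each of left-sham and left-active. That makes 80 TBI subjects and 80 controls.

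Section 10, Specific Aim 1.3, then fixes the population for the predictor question: "TBI subjects from Aim 1.1 will be carried forward for study in Aim 1.3". Specific Aim 2.3 puts the question itself as one of moderation: "Understanding which of the clinical variables described above moderate the efficacy of tDCS in mmTBI".

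Section 11 contains the only power statement for the clinical comparison. "With 40 tDCS treatment patients compared to 40 sham patients" and a standardised effect of 0.7, "we have 80% power to detect effects of active versus sham treatment in a two-sample t-test". It then lists three covariates for the mixed models ("severity: mild vs. moderate, premorbid intelligence: WTAR score, and symptom burden: NSI") and says that including them will determine predictors of response for Aim 1.3. Covariate effects are to be estimated through contrasts in the model. No arm-by-predictor term is named, and the paragraph does not mention Aim 2.3. Section 14 repeats the model description.

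Section 2 (Choice of study population) gives the controls a different purpose: to show that mmTBI patients have cognitive control deficits, and to compare tDCS efficacy between clinical and non-clinical subjects.

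**The concern.** The reason given for the sample does not match the analysis it is meant to serve. Half of the 160 participants are named in a power rationale for an analysis that does not include them. The patients' numbers are supported by a calculation for a different estimand, the overall active-versus-sham difference.

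The model as written may also miss the question. A covariate that shifts the outcome equally in both arms is prognostic. It says nothing about who benefits from tDCS.

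Aims 1.3 and 2.3 are meant to inform patient selection in later applications. A reader who relied on the section 10 sentence could take a significant covariate as a predictor of response, or a non-significant one as shown not to matter, and the plan as written would support neither conclusion.

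**Working it through.** **Inputs.** 40 active and 40 sham TBI patients, effect 0.7 and 80% power come from section 11. Alpha and sidedness are not stated, so two-sided 0.05 is assumed. No attrition rate is given, so none is applied except where noted. Outcome SD is set to 1. No quota for injury severity is set. Section 6 puts about 9,000 of 10,000 source injuries (90%) as mild, so splits from 50/50 to 90/10 are shown. No baseline correlation is given, so 0 and 0.7 are shown as assumptions.

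**1. The plan's own figure.** A two-sample t-test with 40 v 40 and effect 0.7 has 87.1% power. The stated 80% is obtained with about 33 per arm (80.0%) or with two-sided alpha 0.025 (79.9%). Under the assumed alpha the stated figure is therefore conservative, and it is not in dispute here. The smallest main effect with 80% power at 40 v 40 is 0.63 SD.

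**2. Who contributes.** Participants (section 10) names TBI subjects and controls in the predictor rationale. Specific Aim 1.3 carries only TBI subjects forward. Specific Aim 2.3 words its question for mmTBI. The predictor sample is therefore 40 v 40 patients, not 80 v 80 participants.

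**3. What is estimated.** Write the outcome as a + b1·arm + b2·X + b3·arm·X. Without the last term, b2 is the association of X with outcome in both arms together, which is prognosis. The difference in tDCS effect by X is b3. The distinction matters for power: with 80 patients a main-effect correlation of tanh(2.80/√77) = 0.31 is detectable, but b3 is much less precise.

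**4. Precision of the interaction.** For a binary predictor with share p, SE = √[2/(40p) + 2/(40(1−p))]. For a continuous predictor per SD, SE = √(2/40). The detectable effect at 80% power is 2.84 × SE (t, 76 df), and the 95% half-width is 1.99 × SE. Baseline adjustment at correlation 0.7 multiplies by √(1 − 0.49) = 0.714.

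| Predictor | SE | Detectable, unadjusted | 95% half-width | Detectable, r = 0.7 |
|---|---|---|---|---|
| Binary 50/50 | √0.200 = 0.447 | 1.27 | 0.89 | 0.91 |
| Binary 80/20 | √0.3125 = 0.559 | 1.59 | 1.11 | 1.13 |
| Binary 90/10 | √0.556 = 0.745 | 2.1 | 1.48 | 1.51 |
| Continuous, per SD | √0.05 = 0.224 | 0.63 | 0.45 | 0.45 |

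The 1.27 here is unrelated to the effect size of the same value that section 10 uses for MR spectroscopy.

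**5. Power for an interaction of 0.7 SD**, as large as the whole assumed treatment effect and unadjusted: 34% at 50/50, 23% at 80/20 and 15% at 90/10. With baseline adjustment at 0.7 and an even split it is 58%.

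**6. Sensitivity.** If the two post-treatment visits are averaged and all visits correlate at 0.7, the residual SD is √(0.85 − 0.49) = 0.60. The even-split figure becomes 1.27 × 0.60 = 0.76 and the continuous figure 0.63 × 0.60 = 0.38. In the other direction, 34 per arm (15% loss) gives 1.36 SD and 0.68 SD per SD without adjustment (normal approximation).

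**The case against.** The other side has several good points.

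- **The sentence in section 10 gives no power figure.** It says only that power is enhanced, and may have meant that using two arms rather than more preserves it. It does not say so, and that reading leaves the controls unexplained. It does mean that no stated predictor power has been shown to be wrong.
- **Controls share most of the predictors.** A reader might infer that controls could never inform the question because symptom burden does not exist in them. The documents do not support that. Section 2 cites the high rate of post-concussive symptoms in healthy people, section 14 collects such symptoms from all participants, and section 16 refers to scanning controls. Only injury severity clearly has no counterpart. What limits the controls is the population set for Aim 1.3.
- **Section 1 might look like a promise of power**, since it says that "certain clinical variables will reliably predict response to tDCS". Those words belong to a list of hypotheses and claim no power.
- **The unadjusted figures are not the planned analysis.** The plan uses mixed models over three visits, and the gain could be substantial, as steps 4 and 6 show. They also depend on the severity split, which pulls the other way.
- **Contrasts in model effects could be meant to include interactions.** That is possible, but the text does not say it.
- **The primary comparison is untouched**, and nothing in the documents says that a null predictor will be read as absence of moderation.

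**Conclusion.** The point holds as a mismatch between rationale, population and model. The stated reason for the group sizes is power to find predictors in mmTBI patients. The controls fall outside that analysis, the clinical power calculation addresses active versus sham only, and the predictors appear only as covariates although moderation is the question.

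Its size depends on assumptions. At 80% power, two-sided 0.05, 40 v 40 and no attrition, the detectable difference in tDCS effect runs from 0.91 SD (even split, correlation 0.7) to 2.1 SD (90/10 split, no adjustment). For a continuous predictor it is 0.45 to 0.63 SD per SD, or about 0.38 if both post-treatment visits are averaged.

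Two stronger readings should be resisted. One is that the plan contains an arithmetic error about predictor power; it states no such figure. The other is that only very large predictor effects can be found. That is fair for an uneven severity split, but too strong for continuous scores under a well-adjusted model. Nor does the point mean that the controls are without use, since section 2 gives them a purpose of their own.

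**What to change.** **Section 10, Participants.** Remove the predictor-power rationale. Justify 40 v 40 TBI patients by the active-versus-sham comparison in section 11, and the controls by the TBI-versus-healthy question in section 2.

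**Section 11, and the repeated text in section 14.** State that for Aims 1.3 and 2.3:
- each predictor is tested in TBI subjects as an arm-by-predictor (by time) interaction;
- the result is reported as an estimate with a 95% confidence interval and labelled exploratory;
- a non-significant interaction is not read as absence of moderation.

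If detectable interactions are quoted, give them with the assumed alpha, attrition, severity split and baseline correlation beside them, not as single fixed values.

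**Cost.** Wording changes and a few model terms, with no extra patients and no change to treatment or visits. The drawback is that the stated property of the design becomes less favourable.

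Powering the interaction instead would be a different trial: an even-split difference of 0.7 SD without baseline adjustment needs 16 × (2.80/0.7)², about 257 patients.
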